7.5 Continuation of therapy after disease progression
 Anecdotal reports indicate that cessation of ibrutinib in patients with B-NHL may contribute to rapid tumor progression. Consequently, it may be beneficial for patients to begin a new treatment regimen after a minimal interval off ibrutinib. To facilitate this, ibrutinib may be continued for up to 4 weeks after documentation of disease progression provided that all other criteria for continuation of treatment are met. Ibrutinib must be stopped at least 24 hours prior to the initiation of the new B-NHL treatment regimen.

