8.0 DOSAGE MODIFICATIONS

8.1 Dose Modification and Dose Delay

Treatment with ibrutinib should be held for any of the toxicities listed below:

- 8.1.1 Grade 4 neutropenia (ANC < 500/mm³)
- 8.1.2 Grade 3 thrombocytopenia (platelets < 50,000/mm³) in the presence of significant bleeding (\geq Grade 2 bleeding)
- 8.1.3 Grade 4 thrombocytopenia (platelets < 25,000/mm³)
- 8.1.4 Grade 3 or Grade 4 nausea, vomiting or diarrhea (if persistent despite optimal antiemetic or antidiarrheal therapy) or any other Grade 4 or unmanageable Grade 3 drug-related toxicities.

The following actions should be taken for drug-related toxicities:

Occurrence of the Same Adverse Event	Action
First	Hold ibrutinib until recovery to Grade ≤ 1 or baseline; may restart at original dose level
Second	Hold ibrutinib until recovery to Grade ≤ 1 or baseline; restart at 1 dose level lower (420 mg daily)
Third	Hold ibrutinib until recovery to Grade ≤ 1 or baseline; restart at 1 dose level lower (280 mg daily)
Fourth	Discontinue ibrutinib

Ibrutinib may be held for a maximum of 21 consecutive days. Ibrutinib should be discontinued if the treatment cannot be resumed within 21 days. Once the ibrutinib dose is reduced because of toxicity, it cannot be re-escalated. No dose escalation of ibrutinib (above 560 mg) is allowed in this study. Refer to section 3.4 for subjects requiring the initiation of anticoagulants while receiving study

drug and for instructions on dose modification or temporary hold during concomitant administration of CYP3A inhibitors or inducers. Refer to section 5.3 for guidance on dose delays during the perioperative period for subjects who require surgical intervention or an invasive procedure while receiving study drug.

If there is a rapid increase in disease burden leading to an "apparent" response of PD after the study drug has been held for at least 7 consecutive days, an assessment response of tumor flare may be assigned instead of PD. Should this occur the patient may remain on study drug if they otherwise meet criteria to continue until the next restaging exam unless there is ongoing evidence of progressive disease before that time despite ongoing treatment. If there is further documented PD on or before the next restaging evaluation the patient will be considered to have PD and the date of PD will be assigned to the initial date tumor flare.

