9.0 STUDY CALENDAR

Required Studies	Screening (within 4 weeks of initiation of treatment)	During treatment	Post Therapy	Follow-up
Physical				
Medical History	X			
Physical Exam	X	X ⁴	X ⁶	X ⁷
Performance Status	X	X ⁴	X ⁶	
Clinical Disease Assessment	X	X ⁴	X ⁶	
Adverse Event Assessment	X	X ⁴	X ⁶	
EKG	X			
Lab				
CBC and differential	X	X ⁴	X ⁶	
Serum creatinine, total bilirubin, SGOT (AST), electrolytes, glucose	X	X ⁴	X ⁶	
Albumin, LDH	X		X ⁶	
Bone marrow studies	X ¹	X ¹		
Pregnancy test	X ²			
Pathologic studies	X			
Radiology				
CT (preferred) or MRI Chest, abdomen and pelvis	X	X ⁵	X ⁶	
FDG-PET (skull base to proximal femur)	X ³	X ⁵		

¹ Bone marrow studies include aspirate and unilateral or bilateral biopsy and should be performed at screening unless approved by the Sponsor-Investigator or Lead Sub-Investigator. If all bone marrow studies are negative at screening, these do not need to be repeated. If bone marrow status is unknown or positive at screening, patients will need to have a bone marrow study to confirm a suspected CR.

² Pregnancy test is only required in women of childbearing potential.

³ May be obtained up to 8 weeks in advance of initiation of therapy (provided no additional anti-cancer therapies are administered during the interval). A Deauville score should be assigned [19].

⁴ At the beginning of therapy (within 3 days), on completion of every cycle (+/- 3 days) during first 9 cycles, then on completion of every 4 cycles (+/- 6 days) thereafter. For the first day of therapy, pre-entry H&P, PS, disease assessment, and adverse event assessment may be used (these do not need to be repeated within 3 days) and labs done within 14 days are acceptable.

⁵ During treatment restaging CT (preferred) or MRI will be performed on completion of every 3 cycles of therapy (+/- 6 days) during the first 9 cycles and on completion of every 8 cycles of therapy (+/- 12 days) thereafter, or as indicated to evaluate clinical suspicion of disease progression. Restaging PET/CT will be performed once during therapy on completion of the first 6 cycles (+/- 6 days). A Deauville score should be assigned [19] when restaging PET is performed.

⁶ Post therapy studies should be done within 28 days after the last dose of ibrutinib. A CT (preferred) or MRI will be obtained if prior imaging was > 21 days of therapy's completion.

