10.3 Response Criteria

For measurement of response, standard 2014 criteria as described in “Recommendations for Initial Evaluation, Staging, and Response Assessment of Hodgkin and Non-Hodgkin Lymphoma: The Lugano Classification” will be used (see Appendix D) [20].

10.4 If a subject who had radiological evidence of PD is clinically stable or improving or exhibiting signs of tumor flare without confirmation of PD by PET or biopsy, the subject may continue treatment with ibrutinib upon approval by the sponsor-investigator.. If tumor flare is suspected, the PI may continue ibrutinib and obtain additional radiological and clinical evaluation at a subsequent disease evaluation visit within 6 weeks, with a determination as to whether ibrutinib should be discontinued (in subjects with evidence of further progression at repeat evaluation) or further treatment provided (in subjects with signs of subsequent tumor shrinkage or stable disease without clinical deterioration).

10.5 Progression-free survival (PFS): PFS will be measured as time from first study drug administration to the first occurrence of disease progression or death from any cause. Data for subjects without disease progression or death will be censored at the date of the last tumor assessment and before the initiation of alternative

anticancer therapy. The estimates will be formed using the all treated population. Progression-free survival will be calculated using assessments by investigators. Kaplan-Meier methodology will be used to estimate event-free curves and corresponding quartiles (including the median).

10.6 Assessment inadequate, objective status unknown: Progression has not been documented and one or more target lesions or other sites of disease have not been assessed or inconsistent methods of assessment were used.

10.7 Bone Marrow Status: Bone marrow status is evaluated as follows:

Positive: Unequivocal cytological or architectural evidence of malignancy.

Negative: No aggregates or only a few well-circumscribed lymphoid aggregates.

Indeterminate: Does not qualify for either Positive or Negative Status. *Note this typically consists of increased number or size of aggregates without cytological or architectural atypia.

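### Section 8.1 gives no PD date for a tumor flare that is never resolved, so Section 10.5 can censor the patient at the flare scan and raise PFS (minor)

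*Combined protocol and SAP*

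**What the plan says.** Section 8.1 deals with rapid growth that looks like PD after ibrutinib has been interrupted for a week or longer. In that case "an assessment response of tumor flare may be assigned instead of PD", and the patient may stay on drug until the next restaging if otherwise eligible. One event reverses the label: "If there is further documented PD on or before the next restaging evaluation the patient will be considered to have PD". Then "the date of PD will be assigned to the initial date tumor flare". Section 8.1 states no other outcome.

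Section 10.5 counts progression or death as the PFS event, by investigator assessment, and adds: "Data for subjects without disease progression or death will be censored at the date of the last tumor assessment". The assessment used must also precede any other anticancer treatment.

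Two notes to the calendar in Section 9.0 bear on whether another scan follows. Footnote 5 puts restaging CT or MRI after every 3 cycles for the first 9 cycles, with extra imaging on clinical suspicion of progression. Footnote 6 says "Post therapy studies should be done within 28 days after the last dose of ibrutinib", but a CT or MRI "will be obtained if prior imaging was > 21 days of" the end of therapy. The follow-up column schedules no CT.

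Section 11.1 lists three alternative successes: ORR of at least 30%, disease control of at least 50%, or median PFS of at least 6 months. Secondary analyses are mainly descriptive. The expansion rule in Section 11.4 uses ORR alone.

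**The concern.** The flare label replaces PD, and only further documented PD restores it. If that never comes, Section 8.1 leaves the patient without progression, and Section 10.5 treats the patient accordingly. Someone who switches therapy, or who is not scanned again and has no later progression or death recorded, is censored at the last assessment. That can be the scan that showed the apparent PD.

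If the growth was real progression, a PFS event has become a censored time for a patient who is doing badly. Such censoring is informative, and its direction is upward. With about 20 patients and a success bar on the median, one reclassified event can decide whether the bar is met.

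**Working it through.** The plan gives no power or error calculation for PFS, so there is no figure to reproduce. The check traces the rules and then sizes the effect.

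**Tracing the rules for a flare-labelled patient**

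- Further PD documented by the next restaging: PD at the flare date. Handled by 8.1.
- Starts new therapy, no further PD documented: censored under 10.5 at the last assessment before that therapy, possibly the flare scan. Not handled by 8.1.
- Never re-imaged, alive, no further PD recorded: censored at the last assessment, possibly the flare scan. Not handled by 8.1.
- Dies before restaging: still an event under 10.5, dated at death instead of at the flare.

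Footnote 6 does not close the second and third paths. A patient who stops ibrutinib within 21 days of the flare scan needs no further scan.

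**Inputs from the documents.** Cycle of 21 days (Schema). CT every 3 cycles (9.0, footnote 5), so at 63, 126 and 189 days, which are weeks 9, 18 and 27, or 2.1, 4.1 and 6.2 months (30.44 days per month). Estimated enrollment 20 (11.3). Bar of 6 months (11.1).

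**Assumptions.** No other events or censoring before week 27. Unresolved flares are censored at the flare scan. The median is the first time that S(t) ≤ 0.5. PDs are dated at scheduled scans unless stated.

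**Kaplan-Meier estimate at week 18, n = 20**

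| PDs (wk 9 + wk 18) | Unresolved flares | S(week 18) | 6-month bar |
|---|---|---|---|
| 5 + 5 | 0 | (15/20)(10/15) = 0.500 | fails, median 4.1 months |
| 5 + 5 | 1 at wk 9 | (16/20)(10/15) = 0.533 | passes |
| 5 + 5 | 1 at wk 18 | (15/20)(11/15) = 0.550 | passes |
| 5 + 6 | 0 | (15/20)(9/15) = 0.450 | fails |
| 5 + 6 | 1 | (16/20)(9/15) = 0.480 or (15/20)(10/15) = 0.500 | fails |
| 5 + 6 | 2 | (17/20)(9/15) = 0.510, (16/20)(10/15) = 0.533 or (15/20)(11/15) = 0.550 | passes |
| 5 + 7 | 2 | 0.453, 0.480 or 0.500 | fails |

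A pass means that the median is not reached before week 27. If the 5 + 5 case without a flare is read by the midpoint convention, with the next event at week 27, the median is (4.14 + 6.21)/2 = 5.2 months and still fails.

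**Chance of passing, exponential PFS, true median 4 months (assumed)**

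- Chance of PD by week 18: 1 − 2^(−4.14/4) = 0.512. Let X, the number of early PDs, be binomial (20, 0.512).
- No flare: the bar is passed if X ≤ 9, with probability 0.3704.
- One unresolved flare: X = 10 can now also pass. P(X = 10) = 0.1752. X = 11 still fails.
- Flare patient drawn from the early PDs: 0.3704 + 0.1752 ≈ 0.55.
- Flare patient drawn from all 20, so among the early PDs with chance 10/20 when X = 10: 0.3704 + 0.5 × 0.1752 ≈ 0.46.

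The same steps give 0.10 rising to 0.15 or 0.20 for a true median of 3 months (P(X = 10) = 0.102), and 0.64 rising to 0.71 or 0.79 for 5 months (P(X = 10) = 0.150). If event times are exact rather than read from scheduled scans, simulation with a 4-month median gives 0.06 rising to 0.09 (drawn from all 20) or 0.13 (drawn from early PDs).

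**Death path.** With 5 + 5 PDs and one flare patient alive at week 18, S(week 18) = 11/20 = 0.550, and it falls to 0.500 at that patient's death. The bar is passed only if death comes at 6.0 months (week 26.1) or later. After a week-18 flare that leaves 27 − 26.1 = 0.9 week before the next restaging, or under 2 weeks with the 6-day window. After a week-9 flare, a death before the week-18 restaging cannot change the result. In simulation with exact event times, a 4-month median and one flare drawn from all 20, a delay of 2.1 months moves the chance only from 5.8% to 6.5%.

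**The case against.** **Existing safeguards.** Documented PD in Section 8.1 is not limited to a scheduled CT. Clinical disease assessment occurs after each of the first 9 cycles and again after therapy, imaging can be done on suspicion, and Section 8.1 withdraws the flare allowance on continuing evidence of progression. A patient who worsens and switches for that reason would ordinarily be recorded as PD and back-dated. This stands, and it narrows the group. It does not remove it, because nothing requires that record before a switch.

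**Not every flare is progression.** Section 8.1 exists for growth on drug withdrawal. For a true withdrawal flare, counting PD would lower PFS wrongly. This stands: the upward bias is conditional on the flare having been true PD.

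**Stronger readings that the documents do not support.**

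- A reader might take Section 7.5, where "Ibrutinib must be stopped at least 24 hours prior to the initiation of the new B-NHL treatment regimen", as a route to a quick switch after a flare. That section concerns patients whose progression is already documented, and they already have a PFS event.
- A reader might give the death path equal weight. Death remains an event and rarely moves the median across 6 months.
- A reader might extend the gap to Section 10.4 or to disease control. Section 10.4 permits continued treatment but does not replace PD, and Appendix D does not allow CT-based stable disease while PD criteria are met.
- A reader might quote the rise to 0.55 alone. It assumes that the flare falls among the early PDs and that every PD is found at a scheduled scan.

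**Conclusion.** The gap is real and minor. Under the rules as written, a flare-labelled patient who switches therapy or is never re-imaged, with no further PD documented, can be censored at a scan that looked like PD. If the flare was true PD, PFS is biased upward.

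Reaching it takes an interruption of a week or more, apparent PD, a discretionary label and no later documentation. The documents give no rate for this, and zero patients is possible. PFS is secondary and descriptive, while ORR and the Section 11.4 expansion rule are largely unaffected. The success call changes only when the observed median lies within one or two patients of 6 months. The illustrative rise from 0.37 to 0.46 or 0.55 rests on the assumed 4-month median, exponential PFS, scan-detected PD and exactly one unresolved flare. The direction is firmer than the size.

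**What to change.** Add one sentence to Section 10.5, with a cross-reference from Section 8.1: a flare-labelled patient who starts new anticancer therapy, dies, or has no later evaluable assessment counts as PD at the flare date. Leave Section 8.1 unchanged for patients who are re-imaged. A test that reversed PD only when a repeat scan falls back below the PD threshold against the pre-flare nadir would override Section 8.1 for a patient re-imaged as stable, and this point does not justify that.

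Report the number of flare labels, and add one PFS sensitivity analysis that takes the first radiological PD as the event.

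The cost is a wording amendment and one extra analysis of scans already collected. A true withdrawal flare that is never re-imaged would count as PD, so PFS may come out slightly less favourable.

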8.2 Dose Modifications for Adverse Reactions

For adverse reactions listed in Table 1, interrupt IMBRUVICA therapy. Once the adverse reaction has improved to Grade 1 or baseline (recovery), follow the recommended dosage modifications.

Table 1. Recommended Dosage Modifications for Adverse Reactions

Adverse Reaction ^{a,b}	Occurrence	Dose Modification for MCL and MZL After Recovery Starting Dose = 560 mg	Dose Modification for CLL/SLL, WM, and cGVHD After Recovery Starting Dose = 420 mg
Grade 2 cardiac failure	First	Restart at 420 mg daily ^c	Restart at 280 mg daily ^c
	Second	Restart at 280 mg daily ^c	Restart at 140 mg daily ^c
	Third	Discontinue IMBRUVICA	Discontinue IMBRUVICA
Grade 3 cardiac arrhythmias	First	Restart at 420 mg daily ^c	Restart at 280 mg daily ^c
	Second	Discontinue IMBRUVICA	Discontinue IMBRUVICA
Grade 3 or 4 cardiac failure Grade 4 cardiac arrhythmias	First	Discontinue IMBRUVICA	Discontinue IMBRUVICA
Other Grade 3 or 4 non-hematological toxicities ^d Grade 3 or 4 neutropenia with infection or fever Grade 4 hematological toxicities	First	Restart at 420 mg daily	Restart at 280 mg daily
	Second	Restart at 280 mg daily	Restart at 140 mg daily
	Third	Discontinue IMBRUVICA	Discontinue IMBRUVICA

^a See *Warnings and Precautions*.

^b Grading based on National Cancer Institute-Common Terminology Criteria for Adverse Events (NCI-CTCAE) criteria, or International Workshop on Chronic Lymphocytic Leukemia (iwCLL) criteria for hematologic toxicities in CLL/SLL.

^c Evaluate the benefit-risk before resuming treatment.

^a For Grade 4 non-hematologic toxicities, evaluate the benefit-risk before resuming treatment. These updated dosage modification recommendations may reduce the occurrence of additional serious events and are intended to improve tolerability for continued Imbruvica treatment.

Summary of updated dosage modification recommendations:

- Resume ibrutinib treatment at a reduced dose for patients who experience specific non-hematologic and hematologic adverse drug reactions, including Grade 2 cardiac failure and Grade 3 cardiac arrhythmias, as outlined in *Table 1*
- Evaluate the benefit-risk before resuming ibrutinib treatment following Grade 2 cardiac failure, Grade 3 cardiac arrhythmias, or other Grade 4 non-hematological adverse reactions
- Discontinue treatment for patients who experience adverse drug reactions of Grade 3 or 4 cardiac failure or Grade 4 cardiac arrhythmia

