PROTOCOL

A Pilot Study of Single-Agent Ibrutinib in Relapsed or Refractory Transformed Indolent B-Cell Non-Hodgkin Lymphoma

Trial of the Fred Hutchinson Cancer Center (FHCC) and the University of Washington (UW)

Supported in part by Janssen Scientific Affairs, LLC

**Protocol Version Date: 07/18/2022
Previous Version Date: 04/23/2020**

SPONSOR-INVESTIGATOR:

[name]
Professor, UW
Member, FHCC
Fred Hutchinson Cancer Center
[name]
[name]
[contact]

Lead Sub-Investigator:
[name]
Acting Instructor, UW
Fred Hutchinson Cancer Center
[name]
[name]
[contact]

PROTOCOL ACTIVITY

Accrual Activated:

Protocol Revision Record:

Original Version: Version 3, Dated 06/17/2014

Amendment #1: Version 4, Dated 10/23/2015

Amendment #2: Version 5, Dated 02/27/2019

Amendment #3: Version 6.0, Dated 04/23/2020

Amendment #4: Version 7.0, Dated 07/18/2022

SCHEMA

Registration

Ibrutinib 560 mg PO taken daily continuously on a 21-day cycle

Continued until intolerance, progressive disease, or the discretion of patient / clinician

Stop ibrutinib

Routine clinical follow-up for up to 5 years

TABLE OF CONTENTS:

1.0	Objectives	5
2.0	Background and Rationale	5
3.0	Drug Information	6
4.0	Staging Criteria	9
5.0	Eligibility Criteria	9
6.0	Registration	12
7.0	Treatment Plan	12
8.0	Dosage Modifications	13
9.0	Study Calendar	16
10.0	Criteria for Evaluation and Endpoint Definitions	17
11.0	Statistical Considerations	18
12.0	Study Monitoring and Reporting Procedures	19
13.0	Elements of Informed Consent	26
14.0	References	27

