1.2 Secondary objectives

- 1.2.1 To determine the tolerability of chronic ibrutinib therapy in this patient population.
- 1.2.2 To determine the disease control rate of this regimen.
- 1.2.3 Evaluate the complete response rate, overall survival, and progression-free survival to single-agent ibrutinib in this patient population.
- 1.2.4 Determine response rate relative to the underlying B-cell histology.

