2.0 BACKGROUND

2.1 Transformed indolent B-cell non-Hodgkin lymphoma

Indolent B-cell non-Hodgkin lymphomas are comprised of several histologic subtypes, including follicular lymphoma (FL), chronic lymphocytic leukemia (CLL), and marginal zone lymphoma (MZL). As a disease class, it is incurable short of allogeneic transplantation and shows a variable natural history. The course is typically slowly progressive at the outset and responsive to cytotoxic and immunologic therapies. Most patients eventually relapse with a disease phenotype that is increasingly resistant to treatment, with shorter intervals of response, over time [1, 2]. At a rate of approximately 3% per year, indolent B-cell non-Hodgkin lymphomas transform into more aggressive malignancies that share a clonal relationship with the original disease [3].

Transformed indolent B-cell non-Hodgkin lymphoma (TIL) is classically diagnosed with histologic demonstration of an increased proportion, compared with the original specimen, of large neoplastic cells. Though typically transformation is to DLBCL, other subtypes, including to unclassifiable B cell lymphoma (BCLU), lymphoblastic lymphoma, and acute lymphocytic leukemia (ALL) also occur [4]. Clinically, transformation is often reflected by a rapid rise in LDH, discordant localized nodal growth, or new B-type symptoms [4, 5]. Treatment paradigms for TIL are dictated by prior therapies and patient characteristics. High dose therapy (HDT) followed by consolidation with autologous stem cell transplantation (ASCT) appears to benefit select patients, with estimates of 5-year overall survival ranging from 37 – 65% [6-9], but this procedure is generally limited to a subset of patients with chemotherapy-sensitive disease and in good physical condition. Involved-field radiotherapy is beneficial in the subset of patients with early stage disease. For cases of relapsed or refractory TIL (R/R TIL), few therapeutic strategies of proven benefit are available. Radioimmunotherapy has activity in a subset of patients with R/R TIL and is approved for this indication; however its role is not yet clearly defined [10].

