5.0 ELIGIBILITY CRITERIA

5.1 Inclusion Criteria

- 5.1.1 Patients must have histologically confirmed transformed indolent B-cell non-Hodgkin lymphoma that is relapsed or refractory to at least one line of therapy.
- 5.1.2 Patients must have a CT (preferred) or MRI scan of the chest, abdomen, and pelvis within 28 days of enrollment.
- 5.1.3 Patients must have measurable disease defined as lesions greater than 1.5 cm that can be accurately measured in two dimensions by CT (preferred), or MRI.
- 5.1.4 Patients must have a PET scan within 56 days of enrollment.
- 5.1.5 Patients must have an ECOG performance status of 0 to 2 (See Appendix B).
- 5.1.6 Patients must be 18 years of age or older.

5.1.7 Hematology values must be within the following limits independent of growth factor or transfusion support:

5.1.7.1 Absolute neutrophil count (ANC) $\geq 1000/\text{mm}^3$ or $\geq 750/\text{mm}^3$ in the setting of marrow involvement by disease.

5.1.7.2 Platelets $\geq 50,000/\text{mm}^3$ or $\geq 30,000/\text{mm}^3$ in the setting of marrow involvement by disease or splenomegaly due to disease.

5.1.8 Biochemical values within the following limits:

5.1.8.1 Alanine aminotransferase (ALT) and aspartate aminotransferase (AST) $\leq 3 \times$ upper limit of normal (ULN)

5.1.8.2 Total bilirubin $\leq 1.5 \times$ ULN unless bilirubin rise is due to Gilbert's syndrome or of non-hepatic origin

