7.0 TREATMENT PLAN

7.1 For treatment or dose-modification related questions, please contact [name] at [contact] or [name] at [contact]. (MedCon may also be used to contact MDs at [contact].)

7.2 Administration of ibrutinib. Ibrutinib is taken orally at a dose of 560 mg daily.

Drug	Dose	Route	Days	Duration
Ibrutinib	560 mg	PO	Once daily	Until disease progression, intolerance, or decision of patient or treating physician

Post Protocol Follow-up

Long-term follow-up will assess survival and disease progression; subjects will be contacted until death, subject withdrawal of consent, lost to follow-up, or study termination by the sponsor-investigator, whichever occurs first.

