12.2.3 Adverse Events of Special Interest

Specific adverse events or groups of adverse events will be followed as part of standard safety monitoring activities. These events will be reported to Janssen Scientific Affairs within 24 hours of awareness irrespective of seriousness (ie, serious and nonserious adverse events) following the procedure described above for serious adverse events and will require enhanced data collection. Specific adverse events of interest include:

1. Major Hemorrhage

Major hemorrhage is defined as any hemorrhagic event that is Grade 3 or greater in severity or that results in 1 of the following: intraocular bleeding causing loss of vision, the need for a transfusion of 2 or more units of red cells or an equivalent amount of whole blood, hospitalization, or prolongation of hospitalization.

2. Intracranial Hemorrhage

Any intracranial hemorrhage adverse event, including subdural hematoma/hemorrhage, epidural hematoma/hemorrhage and intracerebral hemorrhage, of any grade severity, will be captured as an event of special interest.

3. Other Malignancies

In addition to all routine AE reporting, all new malignant tumors, including solid tumors, skin malignancies and hematologic malignancies, are to be reported for

the duration of study treatment and during any protocol-specified follow-up periods including post-progression follow-up for overall survival.

12.2.4 *Pregnancy*

All initial reports of pregnancy must be reported to Janssen Scientific Affairs by the study-site personnel within 24 hours of their knowledge of the event.

Abnormal pregnancy outcomes (eg, spontaneous abortion, stillbirth, and congenital anomaly) are considered serious adverse events and must be reported as a Serious Adverse Event. Any subject who becomes pregnant during the study must discontinue further study treatment.

Because the effect of the study drug on sperm is unknown, pregnancies in partners of male subjects included in the study will be reported by the study-site personnel within 24 hours of their knowledge of the event.

Follow-up information regarding the outcome of the pregnancy and any postnatal sequelae in the infant will be required.

12.2.5 *Grade*

Grade is defined as the severity of the adverse event. The CTCAE Version 4.0 must be used to determine the grade of the adverse event. If toxicity is not listed in the CTCAE use the following general criteria for grading.

- 0 – No adverse event or within normal limits
- 1 – Mild adverse event

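### Table 1 in section 8.2 assigns restart doses by disease and by starting dose together, and for transformed CLL and FL the protocol does not say which governs

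*Combined protocol and SAP*

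**What the plan says.** **Starting dose.** There is one, with no exception by histology. Section 7.2: "Ibrutinib is taken orally at a dose of 560 mg daily". The schema: "Ibrutinib 560 mg PO taken daily continuously on a 21-day cycle".

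**Who is treated.** Section 2.1 describes the indolent lymphomas as a group of subtypes, "including follicular lymphoma (FL), chronic lymphocytic leukemia (CLL), and marginal zone lymphoma (MZL"). Section 5.1.1 admits the transformed disease without restricting the underlying subtype: "Patients must have histologically confirmed transformed indolent B-cell non-Hodgkin lymphoma that is relapsed or refractory to at least one line of therapy". No exclusion in section 5.2 removes transformed CLL or transformed FL. Secondary objective 1.2.4 expects a mix: "Determine response rate relative to the underlying B-cell histology".

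**Table 1.** Section 8.2 tells sites to interrupt treatment for the listed reactions and, after recovery, to follow the table. It has two dose columns. The first is headed for MCL and MZL with a starting dose of 560 mg. The second is headed "Dose Modification for CLL/SLL, WM, and cGVHD After Recovery Starting Dose = 420 mg". Nothing in 8.2 says which column this trial uses, or whether disease or starting dose selects it.

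**Grading.** Footnote b to Table 1 offers NCI-CTCAE or "International Workshop on Chronic Lymphocytic Leukemia (iwCLL) criteria for hematologic toxicities in CLL/SLL". Section 12.1 adopts CTCAE v4.0 for all toxicities, and section 12.2.5 is firmer: "The CTCAE Version 4.0 must be used to determine the grade of the adverse event".

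**The concern.** Each column heading carries two conditions, and in this trial they come apart. No patient starts at 420 mg, so the second heading is never fully met; but one of its diseases, CLL, is an underlying histology that the trial admits. The table gives no rule for a patient who meets one condition of a heading and not the other.

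The table is an instruction, not background. It sits in section 8.0 and directs the dose at which treatment resumes after a serious toxicity. Two sites, or two clinicians at one site, could resume patients with the same starting dose and the same toxicity at different doses, each citing the same table. At stake are patient safety and uniform treatment, and with them a clear reading of tolerability (objective 1.2.1).

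**Working it through.** The plan states no figure to reproduce. The check sets the sections side by side, with simple ratios.

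**Inputs.** Starting dose 560 mg (schema, 7.2); underlying histologies FL, CLL and MZL (2.1); column headings and cells of Table 1 (8.2); dose levels in 8.1; capsule strength 140 mg (3.2).

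**Step 1: which column does each histology reach?**

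| Underlying histology | By disease list | By starting dose | Result |
|---|---|---|---|
| MZL | 560 mg column | 560 mg column | Both keys agree |
| CLL | 420 mg column | 560 mg column | Keys disagree; neither column fits on both |
| FL | Not listed | 560 mg column | Fits on starting dose only |

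Of the three histologies named in 2.1, only MZL is placed without inference.

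**Step 2: where do the columns differ?**

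| Row group in Table 1 | First event (560 / 420 mg column) | Second event (560 / 420 mg column) |
|---|---|---|
| Grade 2 cardiac failure | 420 / 280 mg | 280 / 140 mg |
| Grade 3 arrhythmia | 420 / 280 mg | Discontinue in both |
| Grade 3–4 cardiac failure, Grade 4 arrhythmia | Discontinue in both | – |
| Other severe non-hematologic toxicity, complicated neutropenia, Grade 4 hematologic toxicity | 420 / 280 mg | 280 / 140 mg |

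The columns differ at the first event in three of four row groups and at the second event in two of four. Elsewhere, including the third event where one is listed, both say discontinue.

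**Step 3: size, relative to the 560 mg start.**
- First event: 420/560 = 0.75, a 25% reduction; 280/560 = 0.50, a 50% reduction.
- Second event: 280/560 = 0.50, a 50% reduction; 140/560 = 0.25, a 75% reduction. The two doses differ by a factor of 280/140 = 2.
- Measured from its own starting dose, each column falls by one capsule at the first event: 560 − 420 = 140 mg and 420 − 280 = 140 mg. Applied to a patient who started at 560 mg, the second column falls by 560 − 280 = 280 mg, or two capsules.

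**Step 4: section 8.1.** Its ladder has no split by histology. A first occurrence may resume at full dose, a second resumes at 420 mg, a third at 280 mg, and a fourth stops treatment. The levels below 560 mg are those of the 560 mg column, and 140 mg is not among them. The ladder also differs from Table 1 in what a first event triggers. For a first Grade 4 neutropenia, sections 8.1 and 8.2 together contain three possible restart doses: 560, 420 and 280 mg. Aligning 8.1 with 8.2 on the number of steps would not by itself say which column of Table 1 applies.

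**Step 5: grading.** Footnote b names a second grading system for hematologic toxicity in CLL/SLL; 12.1 and 12.2.5 name one system for everyone. Grade 4 hematologic toxicity is a trigger in Table 1, so the governing system should be unambiguous. The documents print numeric Grade 4 limits in 8.1 (neutrophils below 500/mm³, platelets below 25,000/mm³) but no iwCLL thresholds, so the two systems cannot be compared from this text.

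**The case against.** The strongest reply is that the headings join disease **and** starting dose. A patient who started at 560 mg fails the 420 mg condition outright, so nobody in this trial belongs in the second column. Section 8.1 supports this, because its reduced levels are 420 and 280 mg for all patients. On this view the second column is generic text that was never adapted to the trial. It is also arguable that CLL/SLL in the heading means the disease under treatment. These patients have transformed disease, typically to DLBCL according to 2.1, so the pre-transformation histology might select nothing. Finally, 7.1 names contacts for dose-modification questions.

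Much of this stands. It is why transformed CLL cannot be said to match both columns; it matches each on one key and neither on both. The starting-dose reading is plausible. But the protocol does not state it. If CLL/SLL means only the untransformed disease, the same logic would take transformed MZL out of the first disease list, leaving starting dose as the only working key while the disease labels remain in print. A directive dosing table should not depend on that chain of inference or on a telephone call.

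A reader might go further and infer two things that the documents do not support:

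- **That objective 1.2.4 is confounded by dose.** This would need transformed-CLL patients with a qualifying toxicity before best response, resumed from the lower column, and a lower response at that dose. None of this is documented. Section 11.1 makes the secondary analyses mainly descriptive, and 11.3 estimates about 20 patients in all.
- **That the same cytopenia would receive two different grades.** Without iwCLL thresholds in the documents, no difference can be shown. Only the conflict over which system governs is established.

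**Conclusion.** The point holds as an internal inconsistency that should be corrected. Table 1 is headed for a starting dose that this trial does not use and for disease lists that place only one of the three named histologies cleanly. For transformed CLL, the same toxicity can be read to 420 or 280 mg after a first event and, in two row groups, to 280 or 140 mg after a second. Transformed FL can be placed only by ignoring the disease labels. Footnote b conflicts with 12.1 and 12.2.5 on the grading system, with no demonstrated effect on any grade.

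This rests on two assumptions: that transformed CLL is eligible, which follows from 2.1 and 5.1.1 with no exclusion in 5.2, and that a clinician could reasonably take the disease label as the key. The documents do not say how many transformed-CLL patients are expected, so the number affected is unknown and may be small. The consequence is for safety and uniform treatment. It does not touch the primary response-rate assessment as planned, and it implies no judgment on which dose or column is clinically right.

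**What to change.** In the next amendment:

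1. Reconcile Table 1 with the single starting dose in 7.2 and with the ladder in 8.1.
2. State which modification schedule applies in this trial to each underlying histology, naming FL, CLL and MZL, and covering any other eligible subtype.
3. Make footnote b agree with 12.1 and 12.2.5 on one grading system.

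The choice of column, the dose steps, and whether any column is kept or removed are clinical decisions for the sponsor-investigator.

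The cost is an edit to one table and one footnote, with matching wording in 8.1. Visits, sample size and analyses do not change.
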